- Concentration of inflammatory cytokines in serum and CSF.

- Concentration of safety and potential surrogate efficacy biomarkers in CSF, urine, and serum.
- Concentration of heparan sulfate and heparan sulfate derivatives in urine and CSF
- Brain magnetic resonance imaging (MRI) and auditory brainstem response (ABR), aka Brainstem Auditory Evoked Potentials.

Study Design:

This is a multicenter, multiple-dose, open-label extension of Study HGT-SAN-055 designed to evaluate the long-term safety and clinical activity and biomarker outcomes of intrathecal administration of 3 dose levels (10 mg and 45 mg once per month and 45 mg every other week [EOW]) of rhHNS via an IDDD in patients with MPS IIIA.

Patients will continue in the treatment group as they participated in the HGT-SAN-055 study:

- Group 1: rhHNS administered by IT injection 10 mg once per month for a total of 6 months
- Group 2: rhHNS administered by IT injection 45 mg once per month for a total of 6 months
- Group 3: rhHNS administered by IT injection 45 mg EOW for a total of 6 months

It is anticipated that all patients successfully completing the HGT-SAN-055 study will elect to continue to receive intrathecal (IT) rhHNS per their previous schedule in Study HGT-SAN-055 by consenting to participate, without interruption, in the HGT-SAN-067 extension study. Thus, for nomenclature of chronology purposes, the Baseline Visit for this extension study will be considered to be the first day the patient received his/her IT dose of rhHNS in Study HGT-SAN-055.

Patients whose parents/legal guardians provide written informed consent/assent to participate in this study will check in with the study center 1 day prior to rhHNS dosing for safety assessments on each rhHNS treatment week. If no safety concerns exist, the patient will subsequently receive IT administration of rhHNS on Day 2. Patients will be discharged from the inpatient unit a minimum of 1 day following dosing with rhHNS and when deemed clinically stable by the Investigator. The patient will have already received a standardized battery of neurodevelopmental assessments at the baseline and 6 month time points in the HGT-SAN-055 study. These same assessments and tests will also be performed at 12, 24, 36, and 48 months. Similarly, MRI of the head, ABR testing, CSF sampling via lumbar puncture and any other procedures requiring anesthesia will be performed at 12, 24, 36, and 48 months.

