Patients whose parents/legal guardians provide written informed consent/assent to participate in this study will check in with the study center 1 day prior to rhHNS dosing for safety assessments on each rhHNS treatment week. If no safety concerns exist, the patient will subsequently receive IT administration of rhHNS on Day 2 (± 2 days). Patients will be discharged from the inpatient unit a minimum of 1 day following dosing with rhHNS and when deemed clinically stable by the Investigator.

The patient will have already received a standardized battery of neurodevelopmental assessments at the Baseline and 6-month time points in the HGT-SAN-055 study. These same assessments and tests will be performed at 12, 24, 36, and 48 months. Similarly, MRI of the head, ABR testing, CSF sampling by means of lumbar puncture and any other procedures requiring anesthesia will be performed at 12, 24, 36, and 48 months.

All patients will undergo end of study procedures 30 (\pm 7) days following their last administration of rhHNS. End of study procedures will include a standard battery of clinical laboratory tests (serum chemistry, hematology, and urinalysis) in CSF and blood, protocol specific laboratory testing (eg, anti-rhHNS antibody testing), neurodevelopmental testing, ABR, child health questionnaires, MRI, and concomitant medications and AE monitoring.

All patients will be contacted by telephone for a Final Safety Follow-up, to be conducted at 30 (\pm 7) days after the EOS procedures to collect updated information on adverse events and concomitant medications, therapies, and procedures.

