It is anticipated that the IDDD will be used to obtain CSF samples and to deliver all administrations of rhHNS. However, if a patient's IDDD becomes nonfunctional or infected, it will be replaced so that the patient can remain on study. If use of the IDDD is precluded on a scheduled day of dosing, the IDDD will be declared a failure; no study drug will be administered, nor CSF sample obtained on that visit. Unlike the HGT-SAN-055 study, no study drug will be administered by lumbar puncture in this extension study. Upon declaration of failure, the IDDD will be removed and the patient scheduled for re-implantation of a new IDDD (see [Section 7.11](#)) at the earliest convenience, so that the patient may remain on, or remain as close as possible, to his/her original IT rhHNS dosing schedule. Note: Patients will require 1 week of recovery time from time of re-implantation, during which time the IDDD cannot be used, this may result in a delay in the next scheduled dose of rhHNS. The patient will resume his or her original dosing schedule; no catch-up dosing will occur.

If a patient discontinues the study, is withdrawn from the study, or the study is stopped by the Sponsor, the IDDD will be removed as part of the End of Study Procedures.

An overview of the study appears in [Appendix 1](#) Schedule of Events.

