6.4 Cerebral Spinal Fluid Sample Procedure

A total of 10 mL of CSF will be obtained in two 5 mL aliquots prior to each injection for safety evaluation using the IDDD. A topical anesthetic agent may be applied over the skin covering the IDDD reservoir prior to CSF sampling. However, CSF will not be obtained if use of the IDDD is precluded, with the exception at the EOS visit, when it may be obtained by means of a lumbar puncture (LP). The performance of LP is at the discretion of the Investigator. An intracranial pressure (ICP) measurement will be obtained whenever a LP is performed.

If a lumbar puncture is to be performed, the patient will be anesthetized via general anesthesia with appropriate airway management. Once the patient is anesthetized, a lumbar puncture will be performed and a CSF sample will be obtained.

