7.7.4 Cerebrospinal Fluid Assessments

Cerebrospinal fluid (CSF) samples (10 ml in two 5 ml aliquots; labeled separately and processed according to the study operations manual) will be obtained from patients through an implanted IDDD. Should the IDDD become blocked or undergo mechanical complications, the CSF sample will not be obtained via lumbar puncture (LP), except when part of the EOS visit. The performance of LP is at the discretion of the Investigator. See [Section 6.4](#) for further details.

CSF sample collection, processing, and shipping instructions will be provided in the Laboratory and/or Study Operations Manual. A CSF sample will be reserved for possible exploratory biomarker studies for MPS IIIA disease.

Each CSF sample collected will be assessed for appearance and will be analyzed using the assays listed in Sections 7.7.4.1, 7.7.4.2, and 7.7.4.4. In addition, as more is learned about Sanfilippo CNS pathology and etiology, future exploratory assays of CSF metabolites or protein or RNA may become available in the future (the samples maybe analyzed, if the assays are found applicable) and are thus not presently listed within this protocol.

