7.8 Anesthesia

Administration of anesthesia/sedation will be given prior to obtaining CSF (when the use of the IDDD is precluded – see [Section 6.4](#)), prior to performing the MRI of the head, the ABR, the intracranial pressure (ICP), and the re-implantation of the IDDD (if applicable). See [Appendix 1](#) for the Schedule of Events.

Note: the neurologic exam and the neurocognitive and developmental assessments must be performed prior to the administration of anesthesia.

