8.2.1 Week 1 (Groups 1 and 2); Week 1 and 3 (Group 3)

8.2.1.1 Day 1 (Pre-treatment) Assessments

- Informed consent (Week 1, Month 1 only) prior to study HGT-SAN-067 study procedures
- Physical examination
- Height and weight
- Vital signs
- Hematology
- Serum Chemistry
- Urinalysis
- Neurological Examination (performed prior to the administration of anesthesia and the rhHNS IT injection)
- Concomitant Medications, Therapies, and Procedures
- AE assessments

Note: If the HGT-SAN-055 EOS (or Screening) assessments were performed within 7 days of first intrathecal rhHNS treatment in this study, the pre-treatment assessments described in this section do not need to be completed prior to the first treatment

DAY 1 (PRE-TREATMENT) ADDITIONAL ASSESSMENTS PERFORMED ONLY AT MONTHS 12, 24, 36, AND 48

- Head circumference
- Visual and hearing assessments
- Urine Heparan Sulfate and Heparan Sulfate Derivatives (Group 3: obtained only at first week of each treatment month)
- Serum Heparan Sulfate and Heparan Sulfate Derivatives (Group 3: obtained only at first week of each treatment month)

- Anti-rhHNS antibody testing
- Auditory Brainstem Response (ABR)
- MRI of the head
- Full neurodevelopmental testing (performed prior to the administration of anesthesia and the rhHNS IT injection)
- Children's Sleep Habits Rating Scale
- Child health questionnaire-50
- Child health questionnaire-87
- Infant toddler QOL Questionnaire

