Appendix 1 Schedule of Events

Table 1 Study Assessments for Patients Who Have Received 6 Months of Treatment With rhHNS (Study HGT-SAN-055) (Dose Groups 1 and 2)

Assessment	Screening/ Baseline Visit ⁱ	Week 1 Each Treatment Month			12, 24, 36, and 48 months	End of Study ^f	Safety Follow-up ^h
		Pre-Tx Day 1 ^{a,1}	IT administration Day 2	Day 3 ^d			
Informed Consent/Enrollment		•					
Physical Examination	•	•	•			•	
Height and Weight	•	•				•	
Head Circumference	•				•	•	
Visual and Hearing Assessment					•	•	
ECG	•		• ^b			•	
Vital Signs	•	•	•	•		•	
Hematology	•	•				•	
Serum Chemistry	•	•				•	
Urinalysis	•	•				•	
Urine Heparan Sulfate and Heparan Sulfate Derivatives	•				• ^c	•	
Serum Heparan Sulfate and Heparan Sulfate Derivatives	•				• ^c	•	
Anti-rhHNS antibody testing (serum and CSF) ^j	•				•	•	
Auditory Brainstem Response (ABR)	•				•	•	
MRI of the Head	•				•	•	
CSF Sample Collection ^k	•		• ^c			• ^c	
rhHNS administration ^g			•				
Neurological Examination	•	•	•	•		•	
Full Neurodevelopmental Testing	•				•	•	
Children's Sleep Habits Rating Scale	•				•	•	
Child Health Questionnaire-50	•				•	•	
Child Health Questionnaire-87	•				•	•	
Infant Toddler QOL Questionnaire	•				•	•	

Table 1 Study Assessments for Patients Who Have Received 6 Months of Treatment With rhHNS (Study HGT-SAN-055) (Dose Groups 1 and 2)

Assessment	Screening/ Baseline Visit ⁱ	Week 1 Each Treatment Month			12, 24, 36, and 48 months	End of Study ^f	Safety Follow-up ^h
		Pre-Tx Day 1 ^{a,1}	IT administration Day 2	Day 3 ^d			
Concomitant Medications, Therapies, and Procedures	•	•	•	•		•	•
Adverse Event Monitoring	•	•	•	•		•	•

Abbreviations: ABR = Auditory brainstem response; CSF = cerebrospinal fluid; ECG = electrocardiogram; MRI = Magnetic resonance imaging;
 TX = treatment;

^a Week 1 only, and only performed if >7 days have elapsed since HGT-SAN-055 EOS visit assessments.

^b ECG to be performed following administration of study drug.

^c A total of 10 mLs of CSF will be obtained in two 5 mL aliquots (labeled separately – process according to study operations manual). An attempt will be made to obtain CSF sample via the IDDD prior to each administration of rhHNS and at the End of Study visit. If it is not possible to obtain CSF using the IDDD, the IDDD will be replaced. See [Section 6.4](#) for details.

^d Patients will be discharged when deemed clinically stable by the Investigator.

^e Specimens collected once a month, at Day 1 of the first treatment week.

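### Amendment 1: Section 4.1 and the synopsis require lumbar puncture for CSF at months 12, 24, 36 and 48, against the device route and schedule set elsewhere in the protocol

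*Protocol*

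**What the plan says.** Two places in Amendment 1 name lumbar puncture as an annual procedure. Section 4.1 states: "CSF sampling by means of lumbar puncture and any other procedures requiring anesthesia will be performed at 12, 24, 36, and 48 months". The Study Design part of the synopsis states: "CSF sampling via lumbar puncture and any other procedures requiring anesthesia will be performed at 12, 24, 36, and 48 months". The original protocol carries the same wording in both places.

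Other parts of the same document describe a different route:

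- Section 4.1, IDDD paragraph: "It is anticipated that the IDDD will be used to obtain CSF samples and to deliver all administrations of rhHNS". It adds that if the device cannot be used on a dosing day, no CSF is taken at that visit.
- Section 6.4: 10 mL is drawn through the IDDD before each injection. If the device cannot be used, CSF is not obtained, "with the exception at the EOS visit, when it may be obtained by means of a lumbar puncture (LP"). Lumbar puncture is left to the Investigator's discretion.
- Section 7.7.4: if the device were to "become blocked or undergo mechanical complications, the CSF sample will not be obtained via lumbar puncture (LP), except when part of the EOS visit".
- Section 7.8: anesthesia for CSF is given "prior to obtaining CSF (when the use of the IDDD is precluded").
- Section 8.2.1.2: CSF collection is a Day 2 item, before the injection.
- Appendix 1, Tables 1 and 2: the CSF row is marked at Screening, Day 2 and End of Study, and is blank in the column for months 12, 24, 36 and 48. Footnote c names the IDDD as the route.

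**The concern.** A site cannot follow both sets of instructions. Under Section 4.1 or the synopsis, each child has a lumbar puncture at four annual visits. Under Section 6.4 and Appendix 1, the child has none at those visits, because CSF is already being drawn through the implanted device before every dose.

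The main stake is an invasive procedure in cognitively impaired children that the schedule does not contain. A secondary stake is consistency of the data. Change from baseline in CSF heparan sulfate is a secondary endpoint, analyzed under Section 10.6.2.2 by mean change with a 95% confidence interval. If sites read the protocol differently, lumbar and device samples could be mixed. The protocol does not say whether the two are interchangeable, so I put no size on this.

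**Working it through.** **Step 1. Is the instruction conditional?** In Section 4.1 and the synopsis, lumbar puncture sampling stands in one list with MRI and ABR, under one verb and one set of months. Appendix 1 marks MRI and ABR at exactly those months. Nothing in either sentence limits the puncture to device failure.

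**Step 2. What does the schedule contain at those months?**

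| Item | Section 4.1 / synopsis | Appendix 1, column for months 12, 24, 36, 48 |
|---|---|---|
| MRI of the head | yes | marked |
| ABR | yes | marked |
| CSF by lumbar puncture | yes | not listed |
| CSF sample, any route | - | not marked (Day 2 column instead) |
| Intracranial pressure | - | not listed |

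Sections 6.4 and 7.12 require an intracranial pressure reading whenever a lumbar puncture is done. A schedule built around four annual punctures would be expected to show four such readings, and it shows none.

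**Step 3. Does anything else at those months need a puncture?** Appendix 1 marks "Anti-rhHNS antibody testing (serum and CSF") in the annual column. Section 7.7.4.3 sets aside an aliquot of each CSF sample for antibodies, so the pre-dose device sample can supply it. There is also a parallel in Section 8.1: when Screening is repeated, anesthesia is given for ABR and MRI, yet CSF is still taken through the IDDD.

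**Step 4. Count.** Punctures per child under Section 4.1 = number of listed months = 4. Punctures scheduled in the annual column of Appendix 1 = 0. With the maximum of 12 patients in Section 5.1, the ceiling is 4 x 12 = 48.

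**Step 5. Check against Table 7-1.** The stated CSF totals are 480 mL (Groups 1 and 2) and 960 mL (Group 3).

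- 48 months x 1 dose x 10 mL = 480 mL
- 48 months x 2 doses x 10 mL = 960 mL

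Both match. Four additional 10 mL lumbar samples would give 480 + 40 = 520 mL and 960 + 40 = 1,000 mL, which the table does not state. This is only supportive. A lumbar sample that replaced a device sample would leave the totals unchanged. The totals are also labelled approximate: 28-day cycles over 4 years would give 52 x 10 = 520 mL and 104 x 10 = 1,040 mL.

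**The case against.** A reader might infer that Sections 6.4 and 7.7.4 ban any lumbar puncture outside the end-of-study visit. They do not say that. Both are worded for a device that is precluded or blocked, and neither addresses a planned annual puncture with a working IDDD. This objection stands. The conflict is with the IDDD route and the schedule, not with an outright prohibition.

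A reader might also lean on the list headed "ADDITIONAL ASSESSMENTS PERFORMED ONLY AT MONTHS 12, 24, 36, AND 48" in Section 8.2.1.1, which names no puncture. That is a Day 1 list, and CSF collection belongs to Day 2, so its silence proves little. The blank in the annual column of Appendix 1 is the better evidence.

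Section 7.8 cuts both ways. The same sentence lists intracranial pressure measurement separately among the anesthetized procedures, which implies that some lumbar puncture is foreseen. The end-of-study puncture is enough to explain it.

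Finally, the lumbar wording appears in the synopsis and body of both visible versions, so annual lumbar CSF may have been intended and the schedule may be what is incomplete. The documents do not exclude this. They do make it less likely: a plan that refuses lumbar puncture at treatment visits even when the device fails, and that schedules neither the puncture nor its pressure reading, does not read like one that requires it every year.

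**Conclusion.** The inconsistency is real and should be fixed. The sentences in Section 4.1 and the synopsis are the likelier error. The size is up to 4 unscheduled punctures per child. The figure of 48 is a ceiling, not an expectation: it assumes that all 12 patients enroll, all reach month 48, and every site follows Section 4.1 over Appendix 1, to which Section 4.1 itself refers. Because MRI and ABR at those months already require anesthesia, the added burden is the puncture and not a further anesthetic.

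The conclusion applies to the text of Amendment 1. Whether Amendments 2 to 8 corrected it cannot be checked here.

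**What to change.** Delete the lumbar puncture item from the annual-procedures sentence in Section 4.1 and from its counterpart in the synopsis. Both would then list only MRI of the head, ABR testing and other anesthetized procedures at months 12, 24, 36 and 48.

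The cost is two wording edits. Appendix 1, Table 7-1, the pre-dose IDDD sampling and the planned analyses stay as they are. The one downside is that, if annual lumbar CSF and the accompanying intracranial pressure readings were intended, the edit removes them. The sponsor should therefore confirm the intent when making the change. If they were intended, the puncture and the pressure reading need to be added to Appendix 1, and Sections 6.4, 7.7.4 and 7.8 brought into line.

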4.2 Rationale for Study Design and Control Group

Study HGT-SAN-055 is an ongoing Phase I/II safety and ascending dose ranging study of intrathecal administration of rhHNS via an IDDD, in patients 3 years of age and older with MPS IIIA and early cognitive impairment. This extension study is proposed to continue evaluation of the effects of intrathecal rhHNS administration on long-term safety and clinical outcomes for patients who completed Study HGT-SAN-055 and elected to continue treatment with rhHNS.

4.3 Study Duration and Dates

The study duration will be 4 years.

5 STUDY POPULATION SELECTION

5.1 Study Population

Patients who have completed all study requirements in Study-HGT-SAN-055 and who elected to continue rhHNS treatment will be eligible to participate; a maximum of twelve patients are planned for this study.

5.2 Inclusion Criteria

Each patient must meet the following criteria to be considered eligible for enrollment in this study.

1. Patients must have completed all study requirements and assessments for Study HGT-SAN-055 prior to enrolling in this extension study and must have no safety or medical issues that contraindicate participation.
2. The patient, patient's parent(s), or legally authorized guardian(s) must have voluntarily signed an Institutional Review Board / Independent Ethics Committee-approved informed consent form after all relevant aspects of the study have been explained and discussed with the patient. The guardians' consent and patient's assent, as relevant, must be obtained.
3. The patient has received and tolerated treatment with rhHNS, completed the End of Study visit, and has received at least 80% of the total planned infusions within the last 6 months in study HGT-SAN-055 (ie, at least 5/6 ([Group 1 or 2] or 10/12 infusions [Group 3])).
4. Patients must be medically stable, in the opinion of the Investigator, to accommodate the protocol requirements, including travel, assessments, and IDDD surgery (if necessary for replacement purposes), without placing an undue burden on the patient/patient's family.

5.3 Exclusion Criteria

Subjects will be excluded from the study if there is evidence of any of the following criteria at screening or at anytime during the study:

1. The patient has experienced an adverse reaction to study drug in Study HGT-SAN-055 that contraindicates further treatment with rhHNS.
2. The patient has a known hypersensitivity to the active ingredient or any excipients in rhHNS drug product.
3. The patient has significant non-MPS IIIA related central nervous system (CNS) impairment or behavioral disturbances that would confound the scientific integrity or interpretation of study assessments, as determined by the Investigator.
4. The patient has significant MPS IIIA behavioral-related issues, as determined by the Investigator, which would preclude performance of study neurocognitive and developmental testing procedures.
5. The patient is pregnant, breast feeding, or is a female patient of childbearing potential who will not or cannot comply with the use of an acceptable method of birth control, such as condoms, barrier method, oral contraception, etc.
6. The patient has any known or suspected hypersensitivity to anesthesia or is thought to have an unacceptably high risk for anesthesia due to airway compromise or other conditions.

7. The patient has a history of poorly controlled seizure disorder.
8. The patient is currently receiving psychotropic or other medications, which in the Investigator's opinion, would be likely to substantially confound test results and the dose and regimen of which cannot be kept constant throughout the study.
9. The patient cannot sustain absence from aspirin, non-steroidal medications, or medications that affect blood clotting within 1 week prior to a relevant study-related procedure (eg, device implantation if applicable), or has ingested such medications within 1 week before any procedures in which any change in clotting activity would be deleterious.
10. The patient has received treatment with any investigational drug (other than rhHNS) intended as a treatment for MPS IIIA or used any other intrathecal delivery device other than what was used in Study HGT-SAN-055, within the 30 days prior to, or during the study, or is currently enrolled in another study that involves an investigational drug or device (screening through safety follow-up contact).
11. The patient has received a hematopoietic stem cell or bone marrow transplant.
12. The patient's parent(s), or patient's legal guardian(s) is/are unable to provide consent or the patient cannot provide assent, as appropriate, due to, but not limited to, the inability to understand the nature, scope, and possible consequences of the study, or do/does not agree to comply with the protocol defined schedule of assessments.

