6.8 Concomitant Therapy

All non-protocol treatments and procedures that occur from the time of informed consent (or assent, if applicable) through the safety follow-up contact are regarded as concomitant and will be documented on the appropriate pages of the electronic case report form (eCRF). Concomitant therapy includes medications, therapies/interventions administered to patients, and medical/surgical procedures performed on the patients.

Every effort should be made to keep the patient's symptomatic Sanfilippo syndrome Type A treatment constant throughout the study. However, changes in medications are acceptable if necessary according to clinical judgment. All changes will be recorded on the appropriate eCRF. Concomitant medication will be coded using World Health Organization Drug Reference List (WHODRL).

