- Clinically significant prolonged (eg greater than 24 to 48 hours) worsening in mental status, including development of new focal or non-focal neurological symptoms, or recurrence of a previously stable prior medical problem judged due to study drug or participation that is exclusive of effects from anesthesia.
- Non-compliance, including failure to appear at 1 or more study visits.
- The patient was erroneously included in the study.
- The patient develops an exclusion criterion.
- The study is terminated by the Sponsor.

If a patient or the patient's legal guardian(s), acting on behalf of the patient, discontinues participation in the study, or the patient is discontinued by the Investigator, the Patient Completion/Discontinuation Case Report Form (eCRF) describing the reason for discontinuation must be completed. Any adverse events (AE's) experienced up to the point of discontinuation must be documented on the AE eCRF. If AEs are present when the patient withdraws from the study, the patient will be re-evaluated within 30 days of withdrawal. All ongoing SAEs at the time of withdrawal will be followed until resolution.

At the time of discontinuation or withdrawal, patients will be asked to participate in all safety and efficacy evaluations required for the end of study visit and for the safety follow-up visit. Participation in these EOS procedures will be strongly encouraged, but is voluntary for those patients electing to discontinue from the study. The patient will be scheduled for the removal of the IDDD.

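### Exclusion criteria stay in force during follow-up, so a child who becomes untestable through MPS IIIA can be removed, and assessments that could still be collected then stop

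*Protocol*

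**What the plan says.** Protocol section 5.3 opens its list of exclusion criteria with: "Subjects will be excluded from the study if there is evidence of any of the following criteria at screening or at anytime during the study". The sentence is the same in the original protocol (21 June 2010) and in Amendment 1 (27 January 2011). Amendments 2 to 8 are not in the part available, so whether it persists could not be checked.

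Three of the criteria matter here:
- Criterion 4 reads: "The patient has significant MPS IIIA behavioral-related issues, as determined by the Investigator, which would preclude performance of study neurocognitive and developmental testing procedures".
- Criterion 7: "The patient has a history of poorly controlled seizure disorder".
- Criterion 8 covers psychotropic or other medication which, as judged by the investigator: "would be likely to substantially confound test results and the dose and regimen of which cannot be kept constant throughout the study".

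Section 7.23 includes this among its removal reasons: "The patient develops an exclusion criterion". That list, however, is introduced as grounds that might justify removal, which is weaker than the wording of 5.3. Patients who leave are not replaced. On leaving, they are asked for all end-of-study safety and efficacy evaluations and the safety follow-up. The same section adds: "Participation in these EOS procedures will be strongly encouraged, but is voluntary for those patients electing to discontinue from the study".

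Section 6.8 asks sites to keep symptomatic treatment constant but then says: "However, changes in medications are acceptable if necessary according to clinical judgment".

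Neurodevelopmental testing is scheduled at months 12, 24, 36 and 48 (section 4.1), and section 10.6.2.1 examines change from baseline by dose group.

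**The concern.** The disease background in section 1.1 describes aggression and hyperactivity as features of MPS IIIA, and Appendix 3 describes children whose nervous system becomes progressively more affected. Over up to four years, a child can therefore come to meet criterion 4 because the disease has advanced. A rule meant to protect test quality at entry then becomes a rule for leaving the study that depends on the outcome being measured.

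Two things are at stake. First, once a child has left, the remaining annual visits are not scheduled. Late means on caregiver- or observer-based scales would rest mainly on children who did not reach the trigger. The introduction says that stabilisation may count as clinically meaningful, so a bias in that direction matters. Second, the primary objective is long-term safety, and removal ends long-term observation in children who may be among the most affected.

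The wording also leaves sites unsure whether removal is mandatory or discretionary, and whether a necessary medication change is accepted or is grounds for exclusion.

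**Working it through.** **What the plan fixes.** The only sample-size figure is a maximum of 12 patients, set by roll-over from HGT-SAN-055 (section 10.2). There is no SD, effect size or dropout figure to reproduce. Everything numerical below is illustration on stated assumptions.

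**Passages side by side.**
- Section 5.3 is mandatory in form; section 7.23 is discretionary. Both cover the same event, a criterion met after entry.
- Criterion 8, if it runs throughout, bears on confounding medication that cannot be held constant. Section 6.8 accepts necessary changes. Section 6.9.1 lists the same criterion under prior therapy, which points to an entry rule.
- After discontinuation, sections 7.23, 8.3 and 8.4 provide end-of-study procedures and a safety contact. None schedules the remaining annual assessments.

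**What removal itself costs.** A child meeting criterion 4 cannot perform the BSID-III or KABC-II, so those scores would be missing even if the child stayed. What removal loses are measures that remain obtainable: VABS-II (interview or questionnaire), SBRS (parent-scored), FPSS/TDS (usable at all ages, per Appendix 3) and parent-completed quality-of-life forms.

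**Size, under assumptions.** Let changes be normal with SD 1, and let a fraction f be removed because they are worst on a trigger that has correlation ρ with the change score. None of these values is in the protocol. For large samples:

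bias of the mean among those remaining = ρ × SD × φ(z_f) / (1 − f)

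With f = 3/12 = 0.25: z_f = −0.674, φ(z_f) = 0.318, and 0.318/0.75 = 0.424. So the bias is 0.3 × 0.424 = 0.127 SD at ρ = 0.3 and 0.424 SD at ρ = 1.0.

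Simulation at the actual small sizes (100,000 trials; t-based 95% CI on those remaining) gives:

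| ρ | 1 of 4 removed: bias (SD) | 3 of 12 removed: bias (SD) | 3 of 12 removed: CI coverage |
|---|---|---|---|
| 0.3 | 0.106 | 0.118 | 93.6% |
| 0.5 | 0.171 | 0.196 | 90.7% |
| 0.7 | 0.242 | 0.274 | 85.7% |
| 1.0 | 0.344 | 0.392 | 69.3% |

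The group size of 4 assumes an equal split of 12 over three dose groups. For scale, the 95% CI half-width with nobody removed, t(0.975, n − 1)/√n, is 1.59 SD at n = 4 and 0.64 SD at n = 12. In a single dose group the bias is small beside the sampling uncertainty; pooled over 12 it is less so.

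**The case against.** A reader might infer that children are removed whenever their disease progresses, and that efficacy is then computed only on those who did well. The protocol does not support that. No criterion names progression or cognitive decline as such: a child who declines but stays testable is not caught by criterion 4. The analysis population in section 10.3 is every eligible patient who agreed to take part, not completers, so data up to removal count.

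A reader might also infer that removal is followed only by an optional exit visit. The optional wording is limited to patients who elect to discontinue; a child removed by the investigator has not elected to. Section 8.3 says that those who discontinue early have the end-of-study assessments. Section 7.23 provides for re-evaluation of adverse events present at withdrawal and follow-up of ongoing serious ones to resolution.

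Further points stand. The neurocognitive scores of an untestable child are lost with or without removal. Criterion 8 and section 6.8 are in tension rather than flat contradiction, since criterion 8 requires both substantial confounding and a regimen that cannot be held constant. Methods are descriptive, tests exploratory and efficacy secondary. Handling of missing values may be in the SAP, which is not shown.

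What remains is that the removal rule is fixed in the protocol, and no analysis plan can recover assessments that were never scheduled.

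**Conclusion.** The point holds in limited form. Applying criterion 4 throughout follow-up allows removal to be triggered by a manifestation of MPS IIIA, and the remaining annual assessments then cease. For scales that could still be collected, late change from baseline would be tilted toward stabilisation. Long-term observation for new safety events also ends in the children removed.

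The direction follows if the trigger is positively related to decline. The size cannot be taken from the protocol. The illustrative ranges are 0.11 to 0.34 SD for 1 of 4 removed and 0.12 to 0.39 SD for 3 of 12. The upper ends require the removed children to be exactly the worst decliners, so they should not be read as expected values. Because the affected read-out is secondary and exploratory, this merits correction but does not undermine the trial's primary descriptive purpose. The conclusion applies to the original protocol and Amendment 1 only.

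**What to change.** - Reconcile the mandatory wording of section 5.3 with the discretionary list in section 7.23, and criterion 8 with section 6.8.
- State whether criteria 4 and 8, which protect test quality, apply only at entry. Criterion 3 concerns impairment unrelated to MPS IIIA and raises no such problem.
- Separate stopping study drug from leaving the study. Ask families of children who stop to continue adverse-event contacts and the annual caregiver- or observer-rated scales (VABS-II, SBRS, FPSS/TDS, caregiver-reported quality of life).
- Report the number of untestable children at each visit.

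Whether drug continues is a clinical decision for the sponsor and investigators and is not addressed here. The cost is amendment wording and a modest follow-up burden for a few families among at most 12. If children who leave were still assessed and analysed at the scheduled visits, the selection effect on these scales would disappear, and no sample size or alpha would change.
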